#### Overview of Experimental Procedures.

Visit 1 Procedures: Informed Consent, screening and Assessments. Participants will be introduced to the study procedures and asked to sign an informed consent approved by the Medical University of South Carolina Institutional Review Board, prior to official enrollment in the study. Following informed consent, a series of assessments designed to evaluate cocaine dependence and use, psychiatric conditions, and mood will be given to the participants. These include a health and physical examine conducted with the study physician or physician's assistant, urine pregnancy test for females, a urine drug screen, CIWA-Ar, standard MUSC clinical intake evaluation screen for clinical substance dependence research which includes medical history (used by the PI), MINI International Neuropsychiatric Interview [17], TLFB for cocaine, alcohol, and marijuana [18], Center for Epidemiologic Studies Depression Scale (CES-D), State-Trait Anxiety Inventory [19], Profile of Mood States [20], cocaine craving inventory [21], Fagerström Test of Nicotine Dependence [22] & Modified Cigarette Evaluation Questionnaire [23], alcohol use inventory (AUDIT)[24], computer based tests of behavioral value. Though these are not primary outcomes, the results will be used in post-hoc analyses of the data. Surveys will be filled out by the patient on tablet computers and data entry done directly via Redcap Software to prevent data loss.

Visit 2 Procedures (MRI 1, Medication initiation). Participants will undergo a baseline MRI scanning session and the following sequences will be collected:

- T1 MPRAGE (5 min). High-resolution structural scans will be obtained using an inversion recovery GeneRalized Autocalibrating Partial Parallel Acquisition (GRAPPA) sequence, 192 slices, voxel size:  $1.0 \times 1.0 \times 1.0$  mm, field of view: 256 mm, section thickness: 1.0 mm with no gap, giving an in-plane resolution of 256. This sequence will be used for anatomic overlays of the functional data and spatial normalization to a standard atlas, TMS coil positioning, and subsequent voxel-based morphometry. Field Map (1 min) Field Map calculations allow for offline correction of imaging distortion during post-processing. Field map configurations will include: flip angle (FA)= 60 degrees, field of view (FOV) = 192 mm; voxel size =  $2.0 \times 2.0 \times 2.0$  mm, 72 contiguous slices 2.0 mm thick.
- Resting-State Functional Connectivity (24 min). The resting-state scan consists of four 6-minute runs. The first two runs will occur just prior to the cocaine cue reactivity task and the last two resting-state runs will occur immediately after the cocaine cue reactivity task. All participants will be asked to keep their eyes open and to not fall asleep. Participant's wakefulness during resting-state scans through the use of a) respiratory and heart rate signal and b) eye movement monitoring, in order to ensure participants are not sleeping. Data processing. Resting-state functional connectivity (rsFC) will be assessed using the in-house scripts with MATLAB and FSL. First, experimental design variables, pre-processed functional images filtered with a 0.01 to 0.08 Hz band-pass filter, and segmented images will be uploaded into the toolbox. 5-mm radius spheres will be created around a priori regions of interest (ROIs) (nucleus accumbens,

mPFC). Individuals' WM and CSF templates, heart-rate (HR), respiration rate and movement parameters will be included as covariates. rZ scores for each person will be generated and entered into statistical models.

- Functional MRI Cocaine Cue Reactivity Task (24 min). This task has been used in 4 original research publications by our group and reliably activates orbitofrontal and medial prefrontal regions [26-28]. They will receive two 12m runs of the task (randomized, counterbalanced order within groups). During both runs they will be instructed to 'allow' themselves to crave (passive limbic engagement). When the task begins participants are shown pseudorandomly interspersed blocks of images: 1) cocaine images (COC), 2) neutral images (NEU), and 3) pleasant images (PLE), all NEU and PLE images will be chromatically matched to the COC images. Stimuli are presented in six blocks across two runs, with each block lasting 3 min and 43 sec per image type (two blocks each of COC, NEU, PLE). Each block is followed by a 6-s washout period, allowing the hemodynamic response from the previous block to decline before the next is presented. Scanning parameters: Multislice gradient-echo echo planar imaging (TR=2000, TE=36 msec, field of view of 207 mm, voxel size 2.0 x 2.0 x 2.0 mm, 69 slices, 2 mm thickness, no skip).

Visit 3 Procedures (MRI 2, cTBS, MRI 3). Following three full days of study medication for the pretreatment arm or at least 24 hrs for the no pretreatment arm, participants will return to the lab and undergo MRI and cTBS procedures as outlined below:

- T1 MPRAGE, Field Map, Resting-State Functional Connectivity, and Cocaine Cue Reactivity task (MRI 2): These scans will be repeated exactly as done in Visit 2.
- Continuous Theta Burst Stimulation to the mPFC (5 min). The cTBS treatment lasts 5 minutes and will be given before the group therapy session. Detailed descriptions of the real and active sham cTBS paradigm have been reported elsewhere [8-9]. After the MRI scans participants will be escorted into the Brain Stimulation room (30 feet away) where the TMS procedure will be performed. TMS will be administered using a neuronavigational targeting approach via the Brainsight imaging system (Rogue Industries). This method allows for the integration of participant's individual structural brain images and synchronizes these images in the real-life 3-D setting using infrared cameras and sensors that enable the TMS operator to precisely administer magnetic fields to an individual's precise brain target with sub-5mm accuracy. Furthermore, functional brain targets may be incorporated in the structural imagery in order to create a network-based personalized treatment approach. This system is safe and does not add any further risk to the participant - it simply requires the participant to wear a headband containing infrared sensors to be tracked in real-time by the camera. No pictures or video will be recorded by the camera, simply the reflections of the infrared laser that return to the camera after coming in contact with sensors which detect movement in the 3-D space. We will then determine the participant's resting motor threshold (RMT, the minimal amount of stimulation required over the hand area of the primary motor cortex to induce contraction of the APB muscle of the hand 50% of the time) via the standardized PEST procedure [29]. During each TMS session, we will take a non-identifiable photo of the participants' forehead (eyes covered with an index card) to ensure the coil is correctly placed each time they return to the lab. The procedures for acquiring the motor threshold, performing cortical localization, standardized procedures, blinding, establishing standardized paradigms and training regimens for all staff, as well as safety and ring the experimental procedures are consistent with our prior publications [8-9, 27,30-32]. We will also publish a Standard Operating Procedure document and video file as supplementary material with any publications that arise from this project. For continuous theta burst stimulation, participants will receive stimulation over the left frontal pole (FP1) (each train: 3 pulse bursts presented at 5Hz, 15 pulses/sec, 600 pulses/train, 60 sec intertrain interval; 110% RMT, MagPro) using a figure 8 coil (Coil Cool-B65 A/P). This protocol has been shown to attenuate BOLD activation in the mPFC and striatum in cocaine dependent individuals in the past [8-9].

Briefly, two trains of either real or sham LTD-like cTBS will be applied over the left frontal pole (EEG 10-20 system: FP1) (1 train: 120 sec, 3 pulse bursts presented at 5Hz, 15 pulses/sec, 1800 pulses/train, 60 sec intertrain interval; 110% RMT, MagPro) using a figure-of- 8 coil (Coil Cool-B65 A/P). During the real and sham cTBS treatment sessions the amplifier output will be escalated (over 30 seconds) from 80% to 110% RMT to enhance tolerability. The MagVenture MagPro system has an integrated, active sham that

passes current through two surface electrodes placed on the scalp. The electrodes will be placed on the left frontalis muscle for all sessions. A patient ID card will randomize participants to receive either real or sham stimulation. This system maintains blinding by a gyroscope in the coil which indicates to the clinical staff whether the coil should be rotated up or down for this participant once the card is entered into the machine. One side of the coil is active, the other is sham. The integrity of the double-blind procedure will be assessed by asking the patients and study personnel rate their confidence regarding their assignment to real or sham TMS (scale 1-10). Immediately after the cTBS session:

- *Confidence in Active or Sham cTBS Assignment (1min)*. Participants will complete a form indicating their confidence (scale 1-10) in whether they are receiving active or sham treatment, and will be prompted to audio record a reason (audio recordings are then transcribed to text, in order to avoid handwriting recognition challenges). Pooled accuracy from prior work in our collaborator's laboratory was 47.6% suggesting that individuals were not aware of the stimulation being received.
- *T1 MPRAGE, Field Map, Resting-State Functional Connectivity, Functional MRI Cocaine Cue Reactivity Task (MRI 3)*: These scans will be repeated exactly as mentioned above for V2 (MRI 1).
- *Behavioral Assessments*. In order to produce a clinically meaningful effect of TBS on behavioral measures such as drug craving, mood, or usage multiple days (and likely multiple weeks of TBS treatment are required). Therefore, brain based dependent measures are the primary outcomes of the study (as they are sensitive to a single day of real versus sham TBS [39]. For the purpose of being thorough however, we will acquire measurements of cocaine craving (Numerical rating scale 1-10) before, 10, 20, 30 minutes after TBS, as well the demand and value of cocaine as a reinforcer using a delayed discounting task and hypothetical purchasing task (before TBS as well as at the conclusion of the TBS visit).
- *Participant compensation*. Participants will be compensated up to \$250 for completion of all study procedures. Participants will receive \$25 at the screening visit, \$80 for the baseline experimental visit and \$80 for the second fMRI scanning session. Participants will receive \$10 for each follow up phone call, up to \$40 for 1 day, 1 week, 2 weeks and 3 weeks after their last visit. Participants will also receive a \$25 bonus for completion of all study visits, follow ups. Compensation will be made for each session completed and will not be contingent upon completion of the entire study. During the informed consent procedure, participants will be notified that they can withdraw from the study at any time under no penalty. Payment will be made for each session completed and will not be contingent upon completion of the entire study. During the informed consent procedure, participants will be notified that they can withdraw from the study at any time under no penalty.
- *DSM Board Plan*: The PIs and Co-I ([name].) will have overall responsibility for safety and data monitoring on a day-to-day basis. The DSMB, as noted below, will provide guidance and input on a scheduled and as-needed basis. As previously mentioned, the DSM Board will meet every 5-7 months with the PI to discuss the information listed in "Content of ME/DSM report". This content of this meeting will be formalized in a report which will be circulated by email and digitally approved by the PI and ME/DSMB. The approved report will be sent to the MUSC IRB, and to the NIH.

## 11.0 Specimen Collection and Banking

Urine samples will be collected for pregnancy testing and drug screening purposes. There will be no identifiers except for a code number on the samples. Urine samples may be stored for point of care for pregnancy testing. A digital key to the code numbers will be maintained in password protected database on the MUSC network. The study PI ([name]) will have access to the password.

## 12.0 Data Management

Prior to formal statistical analysis, summary statistics for all variables will be obtained and spaghetti plots will be generated. All behavioral outcome measures will be based on standardized composite scores from

the literature. We will also use data reduction techniques (such as factor analysis or principle component analysis) to confirm the applicability of the composite scores in our population. In the interests of eventually translating these mechanistic data to a larger clinical trial, we will perform a preliminary Intent-to-Treat analysis on each of the 6 groups to estimate effect sizes for a subsequent power analysis. Analyses will be performed for each phase separately. Image pre-processing will be conducted with FSL v. 5.0: (FMRIB Analysis Group, Oxford, UK) [33] realignment to the first volume, smoothing with an anisotropic 8-mm Gaussian kernel, high-pass filtering, resampling to 2-mm isotropic voxels, and stereotactic registration to the Montreal Neurological Institute 152-subject average template. Subjects with >3 mm movement (total mean frame displacement across the entire task) will be excluded from analysis.

**Specific Aim 1 (cTBS):** Evaluate mPFC cTBS as a tool to modulate corticostriatal rsFC and drug cue-reactivity in treatment-seeking cocaine users.

**Rationale:** Drug cues reliably activate the mPFC & ventral striatum in multiple classes of substance users, including cocaine users. Through an LTD-like form of TBS it is possible to decrease activity in the mPFC and the ventral striatum in chronic cocaine users and alcohol users [9]. **Primary dependent measure:** Change in cue-evoked brain activity and rsFC in corticostriatal circuitry after real but not sham cTBS. **Hypothesis:** LTD-like cTBS to the MPFC of individuals with cocaine use disorder will decrease cocaine cue-reactivity BOLD response in corticostriatal nodes (i.e. mPFC, ventral striatum) and strengthen rsFC between these key nodes.

**Methods and analysis:** Using a standardized cocaine cue-reactivity paradigm we will quantify the percent BOLD signal change in the mPFC and the striatum (dorsal and ventral) as well as several other brain regions with known roles in salience (anterior insula & anterior cingulate), drug cue reactivity, and executive control. This will be achieved by extracting the average BOLD signal timecourse and the percent signal change during the cocaine cue versus neutral cue blocks from *a priori* anatomically defined regions of interest (ROIs), including the striatum (ventral striatum and dorsal striatum), insula, inferior frontal gyrus, and anterior cingulate cortex. Ventral striatal and dorsal striatal ROIs are derived from the FSL Oxford-GSK-Imanova striatal atlas, mapped via probabilistic diffusion tractography [34] in agreement with anatomical projection zones from the frontal cortex [35]. Percent signal change in these areas will be compared between groups receiving real versus sham cTBS (Aim 1). These data will be interpreted relative to changes in a positive (auditory cortex) and a negative (primary visual) control region. We will also perform a whole brain seed-based connectivity analysis with the area under the coil as our seed of interest.

**Alternative outcomes:** Known factors that contribute to variability in brain stimulation treatment response include gender and age (Ziemann & Sieber 2010). Variance in these factors may preclude the detection of a true positive. Consequently, these factors will be included as covariates in the analyses. The scalp-cortex distance will be calculated using Standardized automatic segmentation software developed by our laboratory (BrainRuler 1.0, MATLAB Central repository open source) [36]. From an exploratory hypothesis-generating perspective, for Aims 1 & 2 we will also perform whole brain psychophysiological interaction analyses to evaluate if there are other neural areas that are modulated by TBS that we would have missed in our primary ROI-based strategy.

**RIGOR AND REPRODUCIBILITY: Strategies to Ensure a Robust and Unbiased Approach:** The proposed study will achieve robust and unbiased results via explicit inclusion/exclusion criteria; randomization of treatment condition order and examination of order effects; sham control; double blinding; sophisticated compliance monitoring at MUSC; use of validated MRI, laboratory, and interview/self-report measures; explicit hypotheses; power estimates; planned handling of attrition and missing data; and careful consideration of potential confounds. Methodology is reported in a detailed and fully transparent manner to support replication

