## 1.0 Objectives / Specific Aims

A primary cause of relapse to cocaine use is the high motivation to seek drug produced by cocaine-associated cues. Cue-induced craving is associated with cue-induced elevated corticostriatal activity. Preclinical models demonstrate that decreasing activity in the medial prefrontal cortex (mPFC) and ventral striatum (i.e. nucleus accumbens core), henceforth the “corticostriatal circuit,” can block cue-induced cocaine seeking. As an extension of these preclinical data, the scientific premise of Project 4 is that targeted inhibition of the corticostriatal circuit will dampen cue-induced cocaine craving in individuals with cocaine use disorder.

The overarching goal of this project is to evaluate the efficacy of continuous theta burst stimulation (cTBS) as a tool to restore corticostriatal circuitry function and dampen cocaine cue reactivity among treatment-engaged individuals. cTBS is a non-invasive brain stimulation tool that induces long-term depression (LTD) of neural excitability in the area stimulated and in monosynaptic targets. Recent data from our group demonstrates that a single dose of cTBS to the mPFC selectively decreases activity in the ventral striatum and craving. The efficacy of cTBS as a tool to modulate the striatum depends upon connectivity between the frontal cortex and the striatum. Specifically, the experiments described in this proposal will determine if LTD-like cTBS delivered over mPFC decreases cocaine cue reactivity in individuals with cocaine use disorder. We will evaluate our novel intervention through a double blinded (ACTIVE cTBS vs. SHAM;) study in 160 cocaine dependent individuals. The chance of being randomly assigned to any given group within one of the two treatment arms is 1:1. All individuals will undergo a screening visit (Visit 1; V1), and a baseline fMRI visit (Visit 2; V2) that will assess rsFC and drug cue-reactivity. Following Visit 2, individuals will be randomly assigned to one of 2 to receive either: 1) Active cTBS alone, or 2) Sham cTBS alone. Both groups of participants will undergo a second fMRI visit (Visit 3; V3) that will assess resting-state and drug cue-reactivity: once at the beginning of the session and again immediately following Active cTBS or Sham cTBS. Research staff will follow-up with participants via phone to assess current drug use and craving at 1-day, 1-week, 2-week and 3-weeks post-V3.

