## 4.0 Study Endpoints

Change in fMRI brain response.

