## 10.0 Study Design / Methods

*Overview of study protocol.* The overarching goal of Project 4 within the COCA is to evaluate the efficacy of brain stimulation on addiction pathophysiology in corticostriatal circuitry, and to bidirectionally translate our findings with the preclinical COCA projects that are discovering molecular and physiological mechanisms of cue-induced drug seeking in animal models. Extending prior studies by our team and leveraging the intellectual resources of the COCA faculty, we will investigate the impact of active and sham cTBS on corticostriatal rsFC, drug cue reactivity and craving. This will be achieved through a double blind, active sham- and placebo-controlled study in cocaine users from the community or that have enrolled in an intensive outpatient treatment program (MUSC Center for Drug and Alcohol Programs Intensive Outpatient Program (CDAP-IOP)). Participants will be randomized to receive 3600 pulses of either active or sham cTBS alone without administration of any study medication. The study will require 3 visits while they are enrolled in the study. The cTBS sessions last 5 minutes and will occur immediately before their intensive outpatient visits. Clinical Assessments (see Assessments below) and neuroimaging data will be acquired at 2 timepoints: Baseline (V2) and immediately after cTBS (V3).

*Primary hypotheses:* Real mPFC cTBS will cause a larger decrease in cocaine cue-evoked functional connectivity than sham cTBS. The relationship between baseline rsFC and changes in rsFC will also be investigated as factors that mediate the effects of cTBS cocaine cue reactivity in the striatum and craving.

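### The primary measure is a change, but the scan count conflicts between sections and the analysis never names the pre-stimulation reference scan

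*Combined protocol and SAP*

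**What the plan says.** All references are to the combined protocol and SAP.

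**The outcome is a change.** Section 4.0 gives the endpoint as "Change in fMRI brain response". Section 12.0 gives the primary dependent measure as "Change in cue-evoked brain activity and rsFC in corticostriatal circuitry after real but not sham cTBS". Neither says which scan the change starts from.

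**The scan count differs between sections.** The overview in section 10.0 says that "neuroimaging data will be acquired at 2 timepoints: Baseline (V2) and immediately after cTBS (V3". Section 1.0 also describes Visit 2 as "a baseline fMRI visit (Visit 2; V2) that will assess rsFC and drug cue-reactivity", but then has participants scanned at Visit 3 "once at the beginning of the session and again immediately following Active cTBS or Sham cTBS". Section 8.0 likewise places an MRI on each side of stimulation at Visit 3. The Visit 2 and Visit 3 procedures in section 10.0 number the sessions MRI 1 (Visit 2), MRI 2 (Visit 3, before cTBS) and MRI 3 (Visit 3, after cTBS), with the same sequences each time.

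**The analysis.** Section 12.0 extracts "the percent signal change during the cocaine cue versus neutral cue blocks" from each region of interest and continues: "Percent signal change in these areas will be compared between groups receiving real versus sham cTBS (Aim 1". On gender and age it says: "Consequently, these factors will be included as covariates in the analyses". It names no other covariate.

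**The power paragraph (section 10.0).** It uses two time points and an ICC of 0.8 without identifying the scans. Its pilot data were taken just before and just after real or sham cTBS.

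**The concern.** MRI 1 and MRI 2 both precede stimulation and contain the same sequences, so either can serve as the starting point of the change. The overview points to MRI 1. The pilot behind the power calculation points to MRI 2. Section 12.0 does not decide between them, and its percent signal change is a contrast between cue types within one scan, so the term itself does not identify a pre-post pair.

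Two things are at stake. The first is precision: a plain change score is less efficient than adjusting the post-cTBS value for a pre-cTBS value already in hand. The second is that an unnamed reference can be settled after the results are known. Bias is not at issue for any one reference fixed in advance, because assignment is random.

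**Working it through.** **Inputs**
- ICC 0.8 and two time points: power paragraph, section 10.0.
- 144 full data sets, 160 enrolled, 10% loss: section 6.0. Two arms: section 1.0. This gives 144 / 2 = 72 per arm. (Section 6.0 also says 24 per group, which does not fit two arms; that is a separate matter.)
- Assumed, because the plan does not state them: two-sided 0.05, 80% power, and single-scan SD = 1.

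**The plan's own figures.** Design effect = 1 + (2 − 1) × 0.8 = 1.8, as stated. Enrolment = 144 / 0.9 = 160, as stated. Two time points fit either pair of scans (MRI 1 to MRI 3, or MRI 2 to MRI 3), so the figure does not identify the reference.

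**Scan count.** One scan at Visit 2 plus two at Visit 3 is three, against two in the section 10.0 overview.

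**Precision.** Let r be the correlation between the reference scan and MRI 3. The residual variance of the group contrast is:
- change score: 2(1 − r)
- ANCOVA on one pre-cTBS scan: 1 − r²

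The detectable effect is (1.960 + 0.842) × √(2v / 72), where v is the residual variance.

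| r | Change score, v | ANCOVA, v | Reduction |
|---|---|---|---|
| 0.8 (plan's ICC) | 2 × 0.2 = 0.40 | 1 − 0.64 = 0.36 | 10% |
| 0.5 (assumed) | 2 × 0.5 = 1.00 | 1 − 0.25 = 0.75 | 25% |

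At r = 0.8:
- change score: 2.802 × √(0.80 / 72) = 0.295 SD
- ANCOVA: 2.802 × √(0.72 / 72) = 0.280 SD

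Adding MRI 1 as a second covariate, with all correlations at 0.8, gives v = 1 − 2(0.64) / 1.8 = 0.289.

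**Choice of reference after seeing results.** Write Y1, Y2 and Y3 for the three scans, with all correlations 0.8.
- Var(Y3 − Y1) = Var(Y3 − Y2) = 2(1 − 0.8) = 0.40
- Cov(Y3 − Y1, Y3 − Y2) = 1 − 0.8 − 0.8 + 0.8 = 0.20
- Correlation of the two test statistics = 0.20 / 0.40 = 0.5

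With that correlation, the chance that at least one statistic exceeds 1.96 in absolute value under no effect is 9.1% (4,000,000 multivariate normal draws). Simulated t tests at 72 per arm gave 9.0%. If the same-day correlation stays at 0.8 and the Visit 2 correlations fall to 0.7, 0.6 or 0.5, the figure is 9.3%, 9.4% or 9.5%. It therefore depends little on which scans the ICC describes.

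**The case against.** The strongest reply is that the plan is less open than this suggests.

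- **A pre-cTBS value is clearly intended.** A reader might infer from the within-scan definition of percent signal change that the groups are to be compared on the post-cTBS scan alone. The documents do not support that. Section 4.0 and the primary dependent measure both specify a change, and section 12.0 goes on to interpret the results against changes in control regions. A change score also uses the pre-cTBS value already. What is missing is which scan and which model.
- **The pilot points to a reference.** It was measured on either side of stimulation, which matches MRI 2 to MRI 3. That stands as the best evidence in the documents for MRI 2. It does not settle the matter, because sections 1.0 and 10.0 call Visit 2 the baseline. Section 12.0 also says that each phase is analysed separately, but phase is not defined.
- **Nothing proposes picking the better result.** This also stands. Section 17.0 says that the data analysts are blind to arm. Blinding lowers the risk but does not replace prespecification, since coded groups can still be compared. The 9% is a ceiling for one outcome under that behaviour, not the trial's error rate.
- **The precision gain is modest.** At r = 0.8 it is, and preferring ANCOVA is good practice more than correction of an error.

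A reader might also infer that the second pre-cTBS scan is left over from an abandoned medication arm. Sections 1.0 and 8.0 schedule scans before and after stimulation at Visit 3 without mentioning medication, so that does not follow.

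**Conclusion.** The point holds as a gap in specification. The section 10.0 overview contradicts the three-scan schedule, and section 12.0 fixes neither the reference scan nor an adjustment for it. Confidence is high on the conflict; the consequences are moderate.

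Adjusting for one pre-cTBS scan cuts residual variance by 10% against a change score if the plan's ICC of 0.8 applies to that pair of scans, and by 25% if the correlation were 0.5. Both detectable effects at r = 0.8 lie well below the pilot's 0.72 if that value is read in single-scan SD units (an assumption), so power for the planned comparison is not threatened. The type I error figure of about 9% is a worst case for a single outcome.

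A minor, separate point: the primary hypotheses in section 10.0 list baseline rsFC among the factors that mediate the cTBS effect. Visit 2 rsFC is measured before randomisation, so it can moderate that effect but cannot mediate it. The change in rsFC after cTBS remains a legitimate candidate mediator.

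**What to change.** 1. In section 12.0, state: the MRI 3 value of each primary outcome will be analysed by ANCOVA with terms for arm, MRI 2 value, gender and age; MRI 2 is the reference for any change score. The case for MRI 2 is that it is the last scan before stimulation, is taken at the same visit as MRI 3, and matches the pilot.
2. Correct the section 10.0 overview to three scans, and say in the power paragraph which two scans are the time points.
3. MRI 1 may be added as a covariate, provided that participants who lack only MRI 1 are kept in the analysis.
4. Minor: test Visit 2 rsFC as an arm-by-baseline interaction, and keep mediation for the post-cTBS change in rsFC.

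The cost is protocol and SAP wording and one or two degrees of freedom. No new data are needed. Using MRI 1 as well would require a written rule for participants missing that scan.
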